5.7.4 Return or Destruction of Study Drug

At the completion of the study, there will be a final reconciliation of drug shipped, drug dispensed, drug returns, and drug remaining. This reconciliation will be logged on the drug reconciliation form, signed and dated. Any discrepancies noted will be documented and investigated, prior to return or destruction of unused study drug. Drug destroyed on site will be documented in the study files.

6 Study Procedures

6.1 Visit 1

Screening visit:

During this visit, we will do some tests and procedures to see if subjects are eligible to take part in this research study. The study staff will review the results of these tests and procedures. If subjects aren't eligible, the Principal Investigator will tell them why. At this visit we will:

- Patients will have the ability to conduct this visit remotely. If done remotely, vitals and a physical exam will not be conducted. The patient will need to do the blood sample, chest x-ray and electrocardiogram at their local laboratory and send the results to the PI prior to their Day 0 visit. The patient will give the receipts for the tests to the CRC who will process the reimbursements.
- Ask about medical history
- Perform a physical exam, including height, weight, and "vital signs" (blood pressure, temperature, heart and breathing rates)
- Perform a chest x-ray
- Perform an electrocardiogram (ECG)
- Draw a blood sample
- We may take swabs to test for certain fungal and bacterial infections

Test urine for pregnancy if female subject is able to become pregnant

If it isn't known if subject has HIV, Hepatitis B or C, blood tests will need to be done.

6.2 Visit 2

Day 0 Visit we will:

- Perform a physical exam, check vital signs and ask about side effects or health problems since last visit
- Exam skin lesions to note any changes
- Take photographs of skin lesions to document any changes
- Draw blood sample(s)
- Perform skin biopsies (up to three, 3mm and up to one, 6-8mm tissue samples will be taken)
- Dispense study drug
- Test urine for pregnancy if female subject is able to become pregnant

6.3 Visit 3

Week 1 Visit we will:

- Patients will have the ability to conduct this visit via video visit with the provider. If being conducted remotely, vitals, physical exam, skin lesion assessments, and labs will not be conducted. The patient will need to send photos and the PI will conduct the IGA assessment via video visit.
- Perform a physical exam, check vital signs and ask about side effects or health problems since last visit
- Exam skin lesions to note any changes
- Take photographs of skin lesions to document any changes
- Draw a blood sample
- Dispense study drug

7.4 Visit 4

Week 2 Visit we will:

- Perform a physical exam, check vital signs and ask about side effects or health problems since last visit
- Exam skin lesions to note any changes
- Take photographs of skin lesions to document any changes
- Draw blood sample(s)
- Perform skin biopsies (up to two, 3mm and up to one, 6-8mm tissue samples will be taken)
- Dispense study drug

7.5 Visit 5

Week 3 Visit we will:

- Patients will have the ability to conduct this visit via video visit with the provider. If being conducted remotely, vitals, physical exam, skin lesion assessments, and labs will not be conducted. The patient will need to send photos and the PI will conduct the IGA assessment via video visit.
- Give subject a physical exam, check vital signs and ask about side effects or health problems since last visit
- Exam skin lesions to note any changes

- Take photographs of skin lesions to document any changes
- Draw a blood sample
- Dispense study drug

7.6 Visit 6

Week 4 Visit we will:

- Perform a physical exam, check vital signs and ask about side effects or health problems since last visit
- Exam skin lesions to note any changes
- Take photographs of skin lesions to document any changes
- Draw a blood sample
- Perform an ECG
- Dispense study drug
- Test urine for pregnancy if female subject is able to become pregnant

7.7 Visit 7

Week 8 Visit we will:

- Perform a physical exam, check vital signs and ask about side effects or health problems since last visit
- Exam skin lesions to note any changes
- Take photographs of skin lesions to document any changes
- Draw a blood sample
- Dispense study drug
- Test urine for pregnancy if female subject is able to become pregnant

7.8 Visit 8

Week 12 Visit we will:

- Perform a physical exam, check vital signs and ask about side effects or health problems since last visit
- Exam skin lesions to note any changes
- Take photographs of skin lesions to document any changes
- Draw a blood sample
- Dispense study drug
- Test urine for pregnancy if female subject is able to become pregnant

7.9 Visit 9

Week 16 Visit we will:

- Perform a physical exam, check vital signs and ask about side effects or health problems since last visit
- Exam skin lesions to note any changes
- Take photographs of skin lesions to document any changes
- Draw a blood sample
- Dispense study drug
- Test urine for pregnancy if female subject is able to become pregnant

7.10 Visit 10

Week 20 Visit we will:

- Perform a physical exam, check vital signs and ask about side effects or health problems since last visit
- Exam skin lesions to note any changes
- Take photographs of skin lesions to document any changes
- Draw a blood sample
- Dispense study drug
- Test urine for pregnancy if female subject is able to become pregnant

7.11 Visit 11

Week 24 Visit we will:

- Perform a physical exam, check vital signs and ask about side effects or health problems since last visit
- Exam skin lesions to note any changes
- Take photographs of skin lesions to document any changes
- Draw a blood sample
- Dispense study drug
- Test urine for pregnancy if female subject is able to become pregnant

7.12 Visit 12

Week 28 Visit we will:

- Perform a physical exam, check vital signs and ask about side effects or health problems since last visit
- Exam skin lesions to note any changes
- Take photographs of skin lesions to document any changes
- Draw a blood sample
- Test urine for pregnancy if female subject is able to become pregnant

7.13 Visit 13

Week 32 Visit we will:

- Perform a physical exam, check vital signs and ask about side effects or health problems since last visit
- Exam skin lesions to note any changes
- Take photographs of skin lesions to document any changes
- Draw a blood sample
- Test urine for pregnancy if female subject is able to become pregnant

7 Statistical Plan

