Individuals will then initiate treatment for all lesions of LP once daily and will be evaluated weekly and assessed by PGA of skin, oral mucosa, and hair, BSA, lesion count, Modified CAILS, Pruritus VRS, VAS and NRS scales, Skindex-16, and LPQOL between weeks 0-16 (see Appendix). Week 16 will be the primary endpoint. Therapy will be stopped and the individuals will be evaluated at week 20 after an observation period of 4 weeks and assessed by PGA, BSA, lesion count, mCAILS, Pruritus VRS, VAS and NRS scales, Skindex-16, and LPQOL. Laboratory and safety monitoring will occur at weeks 1, 2, 3, 4, 8, 12, 16, 20, 24, 28, and 32. 3D Photographs will be taken at weeks 0, 1, 2, 3, 4, 8, 12, 16, 20, 24, 28, and 32. Individual lesions will be circled at each visit and the exact area of each lesion will be measured. Up close photos will be taken of the disease.

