week 0 and 2. Blood collection will include the isolation at week 0, 1, 2, 3, 4, 8, 12, 16, 20, 24, 28, and 32. Blood will be drawn into 5mL vials and subsequently separated. The serum and cell pellet will be stored for future analysis. At weeks 0 and 2, an additional 5mL vial of blood will be drawn from patients who agree to provide single-cell RNA sequencing samples. For these samples, the buffy coat (containing peripheral blood mononuclear cells, PBMCs) will be isolated from whole blood, then immediately placed into cryopreservation medium and stored in a -80°C biobank freezer. Up to five skin biopsies will be taken during the study for all patients. At week 0, up to two, 3mm tissue biopsies will be taken from LP lesional skin and one biopsy will be taken from normal appearing skin for bulk RNA sequencing. The initial biopsy of lesional tissue and control will be annotated. At week 2, up to two, 3mm biopsies will be taken – one from normal appearing skin, one from lesional responsive tissue, and/or one from lesional non-responsive tissue. An additional two, 6-8mm biopsies of lesional tissue for single-cell RNA sequencing will be taken—one at week 0 and one at week 2 from patients who opt in. The week 2 biopsy will be obtained from an annotated lesion, whether responsive or non-responsive. Responsive and non-responsive lesions will be determined by the change in mCAILS between week 0 and 2. Responsive tissue will require at least 50% reduction in mCAILS while non-responsive tissue can have progression, no change, or up to a 50% reduction in mCAILS. The lesions will be chosen utilizing full body photographs taken previously at week 0. Up to 60 of the 3mm biopsy samples will be snap frozen and stored in the tissue biobank. Once completed, RNA sequencing will be performed on the tissue samples and analysis will be performed. Paired analysis of treatment responsive and refractory lesions will be made as well as treated and untreated lesions.

Tissue will be collected for bulk RNA sequencing and single cell RNA sequencing (for patients who opt in) at

Nucleic Acid Extractions: RNA will be extracted from a total of 50 µm of fresh tissue using the Qiagen FFPE RNeasy Micro extraction Kit according to manufacturer's recommendation.

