STELARA	Ustekinumab	16 weeks
TALTZ	Ixekizumab	10 weeks
TREMFYA	Guselkumab	12 weeks
XOLAIR	Omalizumab	16 weeks

Table-3: Screening and Visits (+/- 3-day window)

	Screening	Day 0	Week 1	Week 2	Week 3	Week 4	Week 8	Week 12	Week 16	Week 20	Week 24	Week 28	Week 32
Baricitinib (LY3009104)		Х	Х	х	х	Х	Х	Х	Х	Х	Х		
Physical Exam	Х	Х	Х	Х	Х	Х	Х	Х	Х	Х	Х	Х	Х
Adverse Event Assessment		Х	Х	Х	Х	Х	Х	Х	Х	Х	Х	Х	Х
Chest X-ray	Х												
Assessments: PGA, BSA, lesion number, mCAILS, Skindex-16, Pruritus VAS, VRS & NRS, LPQOL		х	х	х	х	х	х	х	х	х	Х	Х	Х
Photographer		Х	х	Х	Х	x	x	x	х	X	Х	Х	Х
Skin Biopsy (tissue/serum bank)		Х		Х									
ECG	Х					Х							
Urine Pregnancy Test	Х	Х				Х	Х	Х	Х	Х	Х	Х	Х
Venipuncture	Х	Х	Х	Х	Х	Х	Х	Х	Х	Х	Х	Х	Х
Biomarker/RNAseq blood (tissue/serum bank)		Х	х	Х	x	х	х	х	х	х	Х	Х	Х
CMP	Х		Х	Х	Х	Х	Х	Х	Х	Х	Х	Х	Х
Lipid Panel	Х		Х	Х	Х	Х	Х	Х	Х	Х	Х	Х	Х
СРК	Х		Х	Х	Х	Х	Х	Х	Х	Х	Х	Х	Х
CBC	Х		Х	Х	Х	Х	Х	Х	Х	Х	Х	Х	Х
Quantiferon Gold	Х												
Hepatitis B	Х												
Hepatitis C	Х												

HIV	Х						
Coccidioidomycosis	Х						

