A serum β -hCG test will be performed in all pre-menopausal women as indicated. All pre-menopausal women who are not sterile at screening will also have a urine pregnancy test performed locally as indicated. Any woman with a confirmed positive pregnancy test during screening is not eligible for the study. A positive urine pregnancy test during the treatment periods of the study requires immediate interruption of study treatment until serum β -hCG is performed and found to be negative. If the serum β -hCG test is positive, study treatment must be definitively discontinued.

Blood Pressure and Pulse:

Height and Weight:

Height and body weight will be measured in indoor clothing, but without shoes. If possible, body weight assessments should be performed by the same study site staff member and using the same scale throughout the study.

Blood Draws:

Subjects should avoid smoking within the hour preceding the blood draws. All laboratory studies will be conducted within the Mayo Clinic Health Systems (Mayo Clinic Arizona and Mayo Clinic Rochester). Details on the collections, shipment of samples and reporting of results will follow Mayo Clinic's current protocols. For the identification of notable values, the Mayo Clinic reference laboratory should be consulted.

Supplemental 3: Safety Monitoring

Infection monitoring:

Study subjects will be evaluated at each visit for signs or symptoms of infection.

- Vitals signs as well as constitutional symptoms will be assessed.
- Assessment for common infections such as cellulitis as well as oral, vaginal, and cutaneous candidiasis will be performed

Post-study Adverse Event

All unresolved adverse events should be followed by the sponsor-investigator until the events are resolved, the subject is lost to follow-up, or the adverse event is otherwise explained. At the last scheduled visit, the sponsor-investigator should instruct each subject to report, to the sponsor-investigator, any subsequent event(s) that the subject, or the subject's personal physician, believes might reasonably be related to participation in this study.

Abnormal Laboratory Values

A clinical laboratory abnormality should be documented as an adverse event if

- they induce clinical signs or symptoms,
- they are considered clinically significant,
- they require therapy.

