The occurrence of adverse events will be sought by non-directive questioning of the patient at each visit during the study. Adverse events also may be detected when the patient volunteers them during or between visits or through physical examination, laboratory test, or other assessments. Please see Supplemental 3 for a detailed description of safety monitoring. Clinically significant abnormal laboratory values or test results will be identified through a review of values outside of normal ranges/clinically notable ranges, significant changes from baseline or the previous visit, or values which are non-typical in patient with underlying disease. Investigators have the responsibility for managing the safety of individual patient and identifying adverse events. Alert ranges for labs and other test abnormalities are included determined by the Mayo Clinic Arizona and Mayo Medical Laboratory. Adverse events will be recorded in the Adverse Events Case Report Form (CRF) under the signs, symptoms or diagnosis associated with them, and severity. All adverse events will be treated appropriately. Once an adverse event is detected, it should be followed until its resolution or until it is judged to be permanent, and assessment should be made at each visit (or more frequently, if necessary) of any changes in severity, the suspected relationship to the study drug, the interventions required to treat it, and the outcome (see Supplemental 3). Information about common side effects already known about the investigational drug can be found in the package insert. This information will be included in the patient informed consent and should be discussed with the patient during the study as needed. The investigator will also instruct each patient to report any new adverse event (beyond the protocol observation period) that the patient, or the patient's personal physician, believes might reasonably be related to study treatment. This information should be recorded in the investigator's source documents, however, if the AE meets the criteria of an SAE. To ensure patient safety, every SAE (see Supplemental 3 for definition), regardless of suspected causality, occurring after the patient has provided informed consent and after the patient begins taking study drug and until 30 days after the patient has stopped study participation will be recorded and reported to Incyte. Any SAEs experienced after this 30-day period should only be reported to Incyte if the investigator suspects a causal relationship to the study drug. All malignant neoplasms will be assessed as serious under "medically significant" if other seriousness criteria are not met. Medical and scientific judgment will be exercised in deciding whether other situations should be considered serious reactions, such as important medical events that might not be immediately life threatening or result in death or hospitalization but might jeopardize the patient or might require intervention to prevent one of the outcomes listed in SAE. Any suspected transmission via a medicinal product of an infectious agent is also considered a serious adverse reaction. All AEs (serious and non-serious) are captured and recorded, SAEs also require individual reporting (see Supplemental 3). To ensure patient safety, each pregnancy occurring while the patient is on study treatment must be reported to the sponsor-investigator within 24 hours of learning of its occurrence. The pregnancy should be followed up to determine outcome, including spontaneous or voluntary termination, details of the birth, and the presence or absence of any birth defects, congenital abnormalities, or maternal and/or newborn complications. Pregnancy follow-up should be recorded on the same form and should include an assessment of the possible relationship to the study treatment. Any SAE experienced during the pregnancy and unrelated to the pregnancy must be reported on a SAE form.

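### Remotely screened patients have their only pre-dose safety bloods from a local laboratory and later ones from Mayo, against the Mayo-only statement, so laboratory change from baseline crosses laboratories

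*Combined protocol and SAP*

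**What the plan says.** Section 6.1 (Visit 1, screening) gives patients the option of a remote visit. In that case: "The patient will need to do the blood sample, chest x-ray and electrocardiogram at their local laboratory and send the results" to the investigator before Day 0.

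Supplemental 2, under Blood Draws, makes no allowance for this: "All laboratory studies will be conducted within the Mayo Clinic Health Systems (Mayo Clinic Arizona and Mayo Clinic Rochester"). It also points to the Mayo reference laboratory for identifying notable values. Sections 3.6 and 8.1 name Supplemental 2 as the place where the baseline screening methods are set out, so its statement covers the same bloods that section 6.1 sends elsewhere.

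On timing, section 3.1 says: "Laboratory and safety monitoring will occur at weeks 1, 2, 3, 4, 8, 12, 16, 20, 24, 28, and 32". Week 0 is not in that list. Table-3 agrees: CMP, lipid panel, CPK and CBC are marked at Screening, blank at Day 0, and marked again from Week 1.

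Section 8.5 lists several ways to identify a clinically significant laboratory result. One of them is "significant changes from baseline or the previous visit".

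**The concern.** For a remotely screened patient, the pre-treatment safety panel and the on-treatment panels come from different laboratories. Any difference in calibration or method between the two enters that patient's change from baseline together with the drug effect.

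The analytes exposed to this include those the drug is expected to move. Section 1.6 reports dose-related rises in CPK, total cholesterol, triglycerides, LDL-C and HDL-C. The trial has one arm of 12, so no comparison group would show the same laboratory switch. A shift between laboratories could be read as a drug effect, or could mask one. Section 7.2 names no adjustment for laboratory, and the plan does not ask for the testing laboratory or its reference range to be recorded.

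**Working it through.** **1. Is there a Mayo pre-dose value that could replace the local one?**

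- Screening: local, if the visit is remote (section 6.1).
- Day 0: Table-3 marks venipuncture and the row "Biomarker/RNAseq blood (tissue/serum bank"), but none of the four safety panels. Section 3.1 says of the drawn blood: "The serum and cell pellet will be stored for future analysis". Section 6.2 lists a blood draw at Day 0 without naming any safety test.
- Week 1: the first scheduled safety panel, already on drug. If Week 1 is a video visit, section 6.3 says "vitals, physical exam, skin lesion assessments, and labs will not be conducted", so the first Mayo panel moves to Week 2.

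No Mayo pre-dose value is planned. Remote Week 1 and Week 3 visits produce no laboratory values at all, so under Supplemental 2 the on-treatment values that do exist are Mayo's.

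**2. Which comparisons cross laboratories?**

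| Use of laboratory values | Crosses laboratories? |
|---|---|
| Section 8.5, change from baseline | Yes, at every on-treatment visit |
| Section 8.5, change from previous visit | Only at the first on-treatment draw |
| Section 8.5, value outside normal or notable range | No, needs no baseline |
| Section 8.1, interruption and discontinuation limits | No, absolute or ULN-based |
| Any descriptive summary of laboratory change | Yes, for the remote patients |
| Primary endpoint, PGA of skin at week 16 | Not a laboratory measure |

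**3. How large could it be?**

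The plan has no figure to reproduce. It gives neither the number of remotely screened patients, k, nor the percentage difference between laboratories, b. Both are assumptions here.

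For one patient, the section 8.5 comparison moves by about that laboratory's own offset. For a mean percent change over n = 12, to a first approximation:

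- Common offset b in all k patients: shift in the mean = (k/12) × b. The sign depends on which laboratory reads higher.
- Independent offsets with mean zero and SD b, each patient using a different laboratory: expected shift = 0, added SD of the mean = b × √k/12.

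| k | b | Common offset: shift (points) | Independent offsets: added SD (points) |
|---|---|---|---|
| 0 | any | 0 | 0 |
| 3 | 5% | 3/12 × 5 = 1.25 | 5 × 1.732/12 = 0.7 |
| 6 | 10% | 6/12 × 10 = 5 | 10 × 2.449/12 = 2.0 |
| 12 | 15% | 12/12 × 15 = 15 | 15 × 3.464/12 = 4.3 |

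The table shows how the answer depends on the assumptions. It does not estimate what will happen in this trial.

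**The case against.** The strongest reply is that no planned analysis is damaged. The objectives and the efficacy endpoints contain no laboratory variable. Section 3.6 names no laboratory change as an endpoint and leaves action on notable values to the investigator's overall judgement. Section 7.2 speaks of numerical outcomes in general and describes the study as meant for estimation. This stands: the effect on analysis is limited to summaries of laboratory change that the plan permits but does not name.

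Section 8.5 also offers alternatives to change from baseline. After the first on-treatment draw, the previous-visit comparison is within Mayo, and the range check needs no baseline. This stands too and narrows the exposure. It does not remove it, because the baseline comparison remains one of the listed routes and the first previous-visit comparison still crosses laboratories.

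A reader might infer a bias of 5 to 15 points in mean laboratory change. The documents do not support that. Such a range needs many remote patients and local laboratories that all differ from Mayo in the same direction. Patients would use their own local laboratories, plausibly different ones, in which case the result is mainly noise. All 12 remote is an extreme case for a single-site study that recruits from the investigators' own practices (section 4.3).

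A reader might also infer that different ULNs at entry and on treatment are themselves a defect. They are not. Expressing a result as a multiple of the testing laboratory's own ULN is the usual way to handle such differences, and the entry limits are checks of eligibility, not measures of change.

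Finally, Mayo here means two sites, Arizona and Rochester, so moving a test to Mayo does not by itself guarantee a single laboratory. That is correct, and the fix has to allow for it.

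**Conclusion.** The point holds in a limited form. Section 6.1 and Supplemental 2 contradict each other and must be reconciled, however many patients are screened remotely. As scheduled, those patients have no Mayo pre-dose CBC, CMP, lipid panel or CPK, so their laboratory change from baseline crosses laboratories in a single-arm trial that cannot separate such a shift from a drug effect.

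The harm is a risk of unknown size, not a demonstrated bias. It depends on k and b, which the documents do not give, and on whether laboratory offsets share a direction. It is negligible if few patients are remote or the laboratories agree. The primary endpoint and the interruption and discontinuation limits are outside its reach. It is worth correcting because the remedy is cheap and a pre-dose baseline cannot be obtained once treatment has begun.

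**What to change.** 1. In Supplemental 2, state the exception for remote screening so that it agrees with section 6.1.
2. In Table-3 and section 6.2, add CBC, CMP, lipid panel and CPK, run at Mayo, to the Day 0 draw for remotely screened patients. The venipuncture is already scheduled, and sections 3.6 and 8.1 already require blood to be drawn before dosing, so no extra visit is needed.
3. Define that Day 0 result as the baseline for laboratory change in these patients. The local result keeps its screening role.
4. Record for every result the testing laboratory, including which Mayo site, and its ULN.

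The cost is at most 12 extra standard panels and one CRF field. Remote screening stays available, and no clinical rule changes.

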3.6 Primary Safety Endpoints

A thorough baseline screening will be followed for all patients and is outlined in Table-2. A detailed list of the methods in which baseline screening will be performed is outlined in Supplemental 2. All blood draws and safety assessments must be performed prior to study treatment administration. Appropriate safety assessments (e.g., evaluation of AEs and SAEs) should be repeated after dosing with study treatment. A physical examination, including general appearance and vital signs, will be performed as indicated in Table-2. If indicated, based on medical history and/or symptoms, additional exams will be performed at the discretion of the investigator. If possible, the same member of the study site staff throughout the study will perform assessments for an individual subject. Information for all physical examinations will be included in the source documentation at the study site. Significant findings that are present prior to the subject signing informed consent will be included in the Medical History. Significant findings made after the signing of the informed consent, which meet the definition of an AE, must be recorded as an AE. Vital signs (blood pressure, pulse, height, weight) will be assessed at each physical examination as indicated in Table-2 (see Supplemental 2 for details on how to acquire vital signs). Whether action needs to be taken to address notable vital signs will be decided by the investigator, considering the overall status of the subject. Laboratory studies will be drawn as indicated in Table-2. Whether action needs to be taken to address notable laboratory values will be decided by the investigator, considering the overall status of the subject. Hematology assessments will be measured at all scheduled study visits specified in Table-2. Serum chemistry will be a comprehensive metabolic and lipid panels that will be measured at all scheduled study visits specified in Table-2.

If the prohibited treatment is being used during the study for any indication, the subject must discontinue use of the prohibited treatment if he/she wishes to continue in the study. In case of undue safety risk for the subject, the subject should discontinue study treatment at the discretion of the investigator/qualified site staff. If the subject received a live virus vaccination during the study, the subject must discontinue study treatment.

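### Remote Week 1 and Week 3 visits waive the scheduled safety labs with no local draw, so the CBC and CMP checks come about 7 days later

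*Combined protocol and SAP*

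**What the plan says.** Three places set the laboratory schedule, none with a remote exception:

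- Section 3.1: "Laboratory and safety monitoring will occur at weeks 1, 2, 3, 4, 8, 12, 16, 20, 24, 28, and 32".
- Section 3.6: "Hematology assessments will be measured at all scheduled study visits specified in Table-2". It says the same of the metabolic and lipid panels. (Table 2 as printed lists biologic washouts; the visit schedule is Table-3, so that must be the table meant.)
- Table-3: CBC, CMP, lipid panel and CPK are marked at Weeks 1, 2, 3, 4, 8, 12 and 16 and at the later visits, with a ±3-day window.

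Sections 6.3 (Week 1) and 7.5 (Week 3) offer a video visit and, in identical words, waive the labs: "If being conducted remotely, vitals, physical exam, skin lesion assessments, and labs will not be conducted". In their place come only patient photographs and a global assessment by video.

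Remote screening in 6.1 is handled differently. The physical exam and vitals are dropped but the blood is kept: "The patient will need to do the blood sample, chest x-ray and electrocardiogram at their local laboratory and send the results to the PI". Costs are covered: "The patient will give the receipts for the tests to the CRC who will process the reimbursements". Supplemental 2, under Blood Draws, places all laboratory work within the Mayo Clinic system and mentions no local exception.

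Section 8.1 sets the limits that need these results. Treatment is interrupted on ANC, ALC or hemoglobin, and permanently stopped on WBC, ANC, lymphocytes or hemoglobin. Seven liver conditions call for the investigator to consider stopping.

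**The concern.** The plan chose weekly safety labs for the first month and then removes half of them for a patient who is remote at both optional visits, without saying so in the schedule. Two things follow.

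First, the sections disagree. Under 3.1 and Table-3 a missing Week 1 CBC looks like a deviation; under 6.3 it is as planned.

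Second, the limits in 8.1 cannot be applied without results, and questions by video cannot reveal a low neutrophil count or a raised transaminase. Section 5.1 puts steady state at about the second to third dose, so Week 1 is the first planned laboratory check at full exposure. A remote patient has that check at Week 2. The protocol already has a local-laboratory route in 6.1 and gives no reason for not using it here.

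**Working it through.** The plan states no figure to reproduce. The check is visit-day arithmetic on Table-3.

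**Inputs.** On-treatment lab visits through Week 16: Weeks 1, 2, 3, 4, 8, 12 and 16 (Table-3). Window ±3 days (Table-3). Remote option at Weeks 1 and 3 only (6.3, 7.5); Weeks 2 and 4 have none (7.4, 7.6). Patients: 12 (3.2).

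**Windows.** Week 1 = Day 4–10; Week 2 = Day 11–17; Week 3 = Day 18–24; Week 4 = Day 25–31; Week 8 = Day 53–59.

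**Delay when a draw is skipped.**
- Week 1 to Week 2: 14 − 7 = 7 days nominal; 11 − 10 = 1 to 17 − 4 = 13 with windows.
- Week 3 to Week 4: 28 − 21 = 7 days nominal; 25 − 24 = 1 to 31 − 18 = 13 with windows.

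The ends of the 1–13 range need the two visits at opposite extremes of their windows.

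| | On-site at both | Remote at both |
|---|---|---|
| First on-drug labs | Day 7 (4–10) | Day 14 (11–17) |
| Draws by Week 4 | 4 | 2 |
| Draws through Week 16 | 7 | 7 − 2 = 5 |
| Week 2 to next draw | 7 days (1–13) | 14 days (8–20) |

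For comparison, the Week 4 to Week 8 spacing is 28 days (53 − 31 = 22 to 59 − 25 = 34) for everyone.

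**Last pre-drug labs to first on-drug labs.** Table-3 marks no CBC or CMP at Day 0. Assume screening labs fall 7 to 28 days before Day 0, from the 1-to-4-week screening period in 3.3. The gap is then 7 + 7 = 14 to 28 + 7 = 35 days on-site, and 7 + 14 = 21 to 28 + 14 = 42 days if Week 1 is remote.

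**How many draws.** At most 12 × 2 = 24, out of 12 × 7 = 84 through Week 16 (28.6%). If half of these visits were remote, 12 of 84 (14.3%). If none, 0. Of the four panels, only CBC and CMP feed the 8.1 limits, so the relevant maximum is 24 × 2 = 48 panels.

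**Margin at entry.** Section 4.2 excludes ANC below 1500, lymphocytes below 1000 and hemoglobin below 10 g/dL. Interruption in 8.1 is at ANC below 1000, ALC below 500 and hemoglobin below 8. A patient at the entry floor must lose more than 500/1500 = one third of ANC, more than 500/1000 = half of ALC, or more than 10 − 8 = 2 g/dL of hemoglobin before a Week 1 draw triggers interruption.

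**The case against.** The waiver is explicit and appears twice. The authors used a local laboratory for remote screening and did not do so here, so this can be read as deliberate. Visit-specific text already overrides general text elsewhere: 6.1 sends screening blood to a local laboratory although Supplemental 2 keeps all laboratory work in-house. On that reading a remote Week 1 without a CBC simply follows 6.3, and a footnote to Table-3 saying labs are not done if remote would end the inconsistency at no cost.

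Much of this stands. The visit text largely answers whether the omission is a deviation, and what remains there is a schedule that does not mention it. But the footnote alone would leave the check a week late, while the 6.1 route would restore it cheaply.

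The clinical objections also carry weight. The blood-count risk is described as low in 1.6, the entry criteria leave margin, and the resulting 14-day spacing is half of what all patients have after Week 4. A reader might count all four panels, up to 24 × 4 = 96, as lost safety checks. The documents do not support that: 8.1 sets no lipid or CPK limit, and 1.6 says such increases have not led to serious events or discontinuation.

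**Conclusion.** The point holds as a minor one. The schedule and the visit instructions conflict, and for a patient remote at both visits the CBC and CMP checks behind 8.1 come about 7 days later, with 2 draws instead of 4 by Week 4. Across the trial this affects 0 to 24 draws, because the remote share is not stated.

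Two stronger readings are tempting. One is that remote patients go unmonitored or that the limits cannot be applied to them. They can: Weeks 2 and 4 are on-site and draw blood, so the checks are delayed, not lost. The other is that a Day 7 draw would catch harm that a Day 14 draw would miss. The steady-state statement in 5.1 is pharmacokinetic, and the documents give no time course for cytopenia or liver injury that would show this. The safety effect is therefore probably small. No planned efficacy comparison uses Week 1 or Week 3.

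The conclusion rests on reading the Table-2 citation in 3.6 as Table-3, and on a value past a limit at the missed visit still being past it at the next draw.

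**What to change.** In 6.3 and 7.5, strike 'and labs' from the waiver and add: *CBC and CMP (lipid panel and CPK optional) will be drawn at a local laboratory within the ±3-day window and before that day's dose. Results go to the PI on receipt, and receipts are reimbursed as in 6.1.* The pre-dose condition follows 3.6: "All blood draws and safety assessments must be performed prior to study treatment administration".

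Add a Table-3 footnote at Weeks 1 and 3: if the visit is remote, CBC and CMP are drawn locally, and lipid panel, CPK and biomarker blood may be omitted. Correct the table reference in 3.6 to Table-3 so that the footnote carries through. In Supplemental 2, add a local-laboratory exception for remote screening and remote Week 1 and Week 3 visits, using that laboratory's reference limits.

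The cost is protocol wording and at most 24 local draws of tests already scheduled, through a route that already exists; the delay returns to 0 days. The downside is that a trip to a local laboratory reduces the convenience of the video visit, and local reference ranges may differ from the site's. How drug is dispensed at a remote visit, which both sections also list, is a separate matter that this change does not settle.
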